**Table 2 Objectives and Corresponding Endpoints (cont.)**

Objective(s)	Corresponding Endpoint(s)
Exploratory Immunogenicity Objectives:	

 
To evaluate potential effects of ADAs
 
	
 
Relationship between ADA status and efficacy, safety, or PK endpoints
 

Biomarker Objectives:	

 
To explore biomarkers that are associated with the efficacy of cobimetinib plus atezolizumab
 
	
 
Genetic alterations, such as RAS mutations, as measured by next generation sequencing
 
Baseline immune contexture, such as TIL distribution, PD-L1 expression, and immune signatures, as measured by IHC and RNA sequencing
 

 
To explore mechanisms of acquired resistance to cobimetinib plus atezolizumab
 
	
 
Genetic alterations, as measured by next generation sequencing
 
Changes in immune contexture, such as TIL distribution, PD-L1 expression, and immune signatures, as measured by IHC and RNA sequencing
 

 
To assess the pharmacodynamic effects of cobimetinib plus atezolizumab treatment
 
	
 
TIL distribution, CD8, PD-L1, and stromal markers as determined by IHC
 
Immune-signatures, pathway activation signature, and stromal signature, as determined by RNA sequencing
 
Changes to circulating IC prevalence and distribution during treatment and at progression
 

ADA = anti-drug antibody; IC = immune cell; IHC = immunohistochemistry; OS = overall survival; PD-L1 = programmed death–ligand 1; PK = pharmacokinetic; TIL = tumor-infiltrating lymphocyte.

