#### **Inclusion Criteria for UC Cohort 5 (Progression while on Anti-PD-1/PD-L1 Therapy):**

- Patients in UC Cohort 5 must meet the following criteria for study entry:
- Histologically or cytologically documented locally advanced (T4b, any N; or any T, N2–N3) or metastatic (M1, Stage IV) urothelial bladder cancer (also termed transitional cell carcinoma, urothelial carcinoma, or carcinoma of the urinary tract; including renal pelvis, ureters, urinary bladder, and urethra)

Patients with mixed histologies are required to have a dominant transitional cell pattern.

- Locally advanced bladder cancer must be inoperable on the basis of involvement of pelvic sidewall or adjacent viscera (clinical stage T4b) or bulky nodal metastasis (N2–N3)

Transurethral resection for bladder tumor (TURBT) specimens must contain a muscle-invasive component (i.e., T2 or greater) or the bladder tumor as verified by local pathology review. If the TURBT specimens do not contain a muscle-invasive component, then specimens obtained at the time of cystectomy, nephroureterectomy, or metastatic spread (i.e., a sample from a metastatic lesion) will be required prior to enrollment.

- Disease progression during or following treatment with at least one platinum-containing regimen for inoperable, locally advanced or metastatic urothelial bladder cancer or disease recurrence
  - Patients who received prior adjuvant/neoadjuvant chemotherapy and progressed within 12 months of treatment with a platinum-containing adjuvant or neoadjuvant regimen are eligible.
  - Patients who have received one cycle of a platinum-containing regimen but discontinued because intolerable toxicity may also be eligible.
  - Patients with disease progression following chemoradiotherapy must demonstrate progression outside the prior radiotherapy port.
- Progression while on a prior anti-PD-1/PD-L1 therapy in the recurrent or metastatic setting
  - Patients are also eligible if they had disease progression on or within 6 months of the last dose of anti-PD-1/PD-L1 therapy in the adjuvant setting
- Prior treatment with T-cell co-stimulating or immune checkpoint blockade therapies, and combinations including anti-CTLA-4, anti-PD-1/PD-L1 therapeutic antibodies are allowed
- Patients are eligible if they received no more than three lines of therapy in the advanced, metastatic setting

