#### **4.5.6.3 Central Laboratory Assessments**

A central laboratory will coordinate the sample collection of tissue and blood samples for research-related testing at central laboratories. Instruction manuals and supply kits will be provided for all central laboratory assessments. Serum samples collected for PK and immunogenicity (anti-drug antibody [ADA]) analysis may be needed for additional PK and ADA assay development and validation, and additional immunogenicity characterization; therefore, these samples will be destroyed no later than 5 years after the final Clinical Study Report has been completed. The schedule for sampling is presented in [Appendix 2](#).

Samples for the following laboratory tests will be sent to one or several central laboratories for analysis:

- Serum samples for immunogenicity (ADA) assessment  
Serum samples will be assayed for the presence of ADAs to atezolizumab with use of validated immunoassays.
- Serum samples for PK analysis  
Serum samples will be assayed for atezolizumab concentration with use of a validated immunoassay.
- Plasma samples for PK analysis  
Plasma samples will be assayed for cobimetinib concentration with use of a validated assay.

- [REDACTED]
- [REDACTED]
- [REDACTED]
- Blood sample for DNA extraction to enable analysis via next-generation sequencing (NGS) and/or optional whole genome sequencing (WGS)
- Tumor tissue sample collected during the study for exploratory research on biomarkers (see [Table 2](#)) and for DNA extraction to enable analysis via NGS

[REDACTED]

NGS may be performed by Foundation Medicine. If performed by Foundation Medicine, the investigator can obtain results from the samples collected at the time of disease progression in the form of an NGS report, which is available upon request directly from Foundation Medicine. The investigator may share and discuss the results with the patient, unless the patient chooses otherwise. The Foundation Medicine NGS assay has not been cleared or approved by health authorities. The NGS report is generated for research purposes and is not provided for the purpose of guiding future treatment decisions.

For sampling procedures, storage conditions, and shipment instructions, see the laboratory manual.

Biological samples will be destroyed when the final Clinical Study Report has been completed, with the following exceptions:

[figure not shown]

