## **6. STATISTICAL CONSIDERATIONS AND ANALYSIS PLAN**

[figure not shown]
This study is designed to explore the preliminary efficacy, safety, pharmacokinetics, immunogenicity, and biomarker of cobimetinib plus atezolizumab in seven patient cohorts with advanced solid tumors, including SCCHN, urothelial carcinoma, and RCC.

The primary analysis will be conducted once all patients in a particular cohort have been followed for a clinically meaningful period of time of approximately 16 weeks. The statistical results will be summarized and presented by cohort.

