## **6.7 IMMUNOGENICITY ANALYSES**

The immunogenicity analyses will include patients with any ADA assessment, with patients grouped according to treatment received.

The number and proportion of ADA-positive patients and ADA-negative patients during both the treatment and follow-up periods will be summarized by treatment group. Patients are considered to be ADA positive if they are ADA negative or missing data at baseline but develop an ADA response following study drug administration (treatment-induced ADA response), or if they are ADA positive at baseline and the titer of one or more post-baseline samples is at least 4-fold greater (i.e.,  $\geq 0.60$ -titer units) than the titer of the baseline sample (treatment-enhanced ADA response). Patients are considered to be ADA negative if they are ADA negative or missing data at baseline, have a post-baseline ADA result, and all post-baseline samples are negative, or if they are ADA positive at baseline but do not have any post-baseline samples with a titer that is at least 4-fold greater than the titer of the baseline sample (treatment unaffected).

The relationship between ADA status and safety, efficacy, PK, and biomarker endpoints may be analyzed and reported descriptively via subgroup analyses.

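### Section 6.7 counts baseline-positive, treatment-unaffected patients as ADA negative, so the exploratory comparisons by ADA status can have antibody carriers in their reference group

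*Combined protocol and SAP*

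**What the plan says.** Section 6.7 gives one definition of ADA status with two outcomes.

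- **Positive.** Either baseline is negative or missing and an ADA response follows (induced), or baseline is positive and "the titer of one or more post-baseline samples is at least 4-fold greater" than baseline (enhanced).
- **Negative.** Either baseline is negative or missing and all later samples are negative, or patients qualify "if they are ADA positive at baseline but do not have any post-baseline samples with a titer that is at least 4-fold greater" than baseline (labelled treatment unaffected).

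The same section continues: "The relationship between ADA status and safety, efficacy, PK, and biomarker endpoints may be analyzed and reported descriptively via subgroup analyses". No other definition of status is offered for that purpose. Table 2 lists the matching exploratory endpoint as "Relationship between ADA status and efficacy, safety, or PK endpoints", under an objective on potential effects of ADAs.

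On who could be positive at baseline: Section 4.1.2.1 excludes prior checkpoint inhibitors in Cohorts 1–3 only. Cohort 5 requires "Progression while on a prior anti-PD-1/PD-L1 therapy in the recurrent or metastatic setting", with an alternative route for progression on or soon after adjuvant use. Cohorts 4 and 6 have similar criteria, and Cohort 7 requires at least two cycles of such therapy. None of these names or excludes a particular agent. On the assay, Section 4.5.6.3 states: "Serum samples will be assayed for the presence of ADAs to atezolizumab with use of validated immunoassays".

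**The concern.** Counting new antibodies and asking what antibodies do are different questions. For the first, a patient whose baseline titer does not rise is correctly left out of the numerator. For the second, the reference group should be free of antibodies. Under Section 6.7, a patient with anti-atezolizumab antibodies before the first infusion and at every later sample serves as a reference for patients with induced antibodies. This happens with complete data; it is not a missing-sample problem.

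If such patients exist and their antibodies matter, a difference in drug levels, response or reactions by ADA status would look smaller than it is. The question is most relevant in pretreated patients, where carriers are also most likely.

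**Working it through.** **The plan's own figure.** Section 6.7 equates a 4-fold rise with 0.60 titer units. On a log10 scale, log10(4) = 0.602, so the cut-off is consistent.

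**Inputs from the documents.** Section 6.1 plans about 20 to 40 patients in each of Cohorts 1–6 and about 12 in Cohort 7. Cohorts 4–7 therefore hold 3 × 20 + 12 = 72 to 3 × 40 + 12 = 132 patients. The maximum total is 6 × 40 + 12 = 252, against the stated approximate 250.

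**Inputs not in the documents (assumed ranges).**
- b, baseline ADA prevalence: 0–30%.
- f, share of baseline-positive patients without a 4-fold rise: 50–100%.
- i, induced ADA among baseline-negative patients: 10–40%.
- Pre-existing ADAs have the same effect as treatment-emergent ADAs.

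**Formula.** Carrier share of the ADA-negative group:

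c = b·f / [b·f + (1 − b)(1 − i)]

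Observed absolute contrast = (1 − c) × true absolute contrast, so c is the proportional loss.

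**Main case, i = 20%, f = 100%.**
- b = 0: c = 0.
- b = 5%: 0.05 / (0.05 + 0.95 × 0.80) = 0.05 / 0.81 = 6%.
- b = 10%: 0.10 / (0.10 + 0.90 × 0.80) = 0.10 / 0.82 = 12%.
- b = 20%: 0.20 / (0.20 + 0.80 × 0.80) = 0.20 / 0.84 = 24%.
- b = 30%: 0.30 / (0.30 + 0.70 × 0.80) = 0.30 / 0.86 = 35%.

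In a 20-patient cohort, these prevalences correspond to 0, 1, 2, 4 and 6 carriers.

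**Sensitivity of the loss.**

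| i | f | b = 5% | b = 10% | b = 20% | b = 30% |
|---|---|---|---|---|---|
| 10% | 100% | 6% | 11% | 22% | 32% |
| 20% | 50% | 3% | 6% | 14% | 21% |
| 40% | 100% | 8% | 16% | 29% | 42% |

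**Pooling.** Section 6.7 says ADA counts "during both the treatment and follow-up periods will be summarized by treatment group", while Section 6 says "The statistical results will be summarized and presented by cohort". If all 252 patients were pooled, with no baseline positives in the 120 patients of Cohorts 1–3, i = 20% and f = 100%, the loss would be 6.6 / (96 + 106.9) = 3% at b = 5% and 39.6 / (96 + 113.5) = 19% at b = 30%.

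**Absolute versus relative.** The rule that the loss equals c holds for absolute differences. Take 6 emergent, 3 unaffected and 11 never-positive patients, with assumed mean trough 100 without and 75 with antibodies. The reference mean is (11 × 100 + 3 × 75) / 14 = 94.6. The absolute difference falls from 25 to 19.6, a loss of 3/14 = 21%. The relative difference goes from −25% to 75/94.6 − 1 = −21%, a loss of about 17%.

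**Who the negative group takes in.** Read literally, it includes two further kinds of baseline-positive patient: those who later turn negative, and those with no post-baseline sample. A post-baseline result is required when baseline is negative or missing, but not when it is positive.

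**The case against.** The strongest reply is that the affected analysis is minor and the bias may not exist. Section 6.7 says the relationship may be analyzed, Table 2 calls it exploratory, and Section 6.1 rules out formal testing. All of that stands.

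The scope is also narrower than prior PD-1/PD-L1 treatment in general. The assay detects antibodies to atezolizumab, so prior nivolumab or pembrolizumab is no documented reason for a positive baseline. The background describes those two agents for SCCHN and nivolumab for RCC. It describes atezolizumab as approved for UC (Sections 1.1.2 and 1.2.4) and non–small cell lung cancer (Section 1.2.4). That makes carriers plausible chiefly in Cohort 5, and perhaps among the 12 patients of Cohort 7. Even in UC, other agents are described. A reader might infer that any ADA effect is diluted throughout Cohorts 4–7; the documents do not support that.

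A reader might also infer that the report would wrongly conclude that ADAs have no effect. That does not follow: under the stated model the contrast shrinks but does not vanish, and with so few ADA-positive patients per cohort a modest shift may not change a descriptive reading.

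Finally, Table 2 already defines the immunogenicity endpoint relative to baseline ADA, and Section 6.7 names the induced, enhanced and unaffected categories. That shows the split is easy to make. It does not require the split in the relationship analyses, nor a table of baseline prevalence.

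**Conclusion.** The grouping does not suit the exploratory objective on effects of ADAs, because its reference group can contain antibody carriers. The size cannot be fixed from the documents. With 20% induced ADA and no boosting, the absolute contrast in affected cohorts loses nothing at zero baseline prevalence, about 6–12% at 5–10%, and 24–35% at 20–30%.

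The direction, toward no difference, rests on pre-existing ADAs acting like emergent ones. For baseline-positive patients who turn negative, that is weaker. If pre-existing ADAs act differently, pooling them with never-positive patients would still hide it.

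The primary ORR analysis and the treatment-emergent ADA incidence are not affected. This is a worthwhile low-cost improvement, not a threat to the trial's main results.

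**What to change.** Keep the Section 6.7 definition for ADA incidence. For the relationship analyses, add that:

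- results are shown for three groups: treatment-emergent (induced or enhanced), baseline-positive treatment-unaffected, and never positive;
- never-positive patients are the reference;
- a post-baseline ADA result is required in all three groups;
- baseline ADA prevalence is tabulated by cohort and by prior atezolizumab use.

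No new samples are needed. Appendix 2 already schedules a sample before the first atezolizumab infusion in every cohort, and Section 4.5.2 collects prior cancer therapies. The cost is a short addition to Section 6.7, one extra column in the relationship tables and the baseline tabulation.

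The downside is a small treatment-unaffected group and a somewhat smaller reference. With 132 patients in Cohorts 4–7, b = 10%, i = 20% and f = 100%, about 13 patients (132 × 0.10) move to their own group and the reference falls from about 108 to 95 (132 × 0.90 × 0.80). Under the model used here, the comparison of emergent with never-positive patients then keeps the full contrast.

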### Schedule of Pharmacokinetic and Immunogenicity Samples

Visit	Timepoint	Sample Type(s)
Day 1 of Cycle 1 (Cohorts 1–6 only)	Prior to atezolizumab infusion	Atezolizumab PK and ADA (serum)
	30 ( $\pm$ 10) minutes following end of atezolizumab infusion	Atezolizumab PK (serum)
Day 15 of Cycle 1 (Cohort 7 only)	Prior to atezolizumab infusion	Atezolizumab PK and ADA (serum)
	30 ( $\pm$ 10) minutes following end of atezolizumab infusion	Atezolizumab PK (serum)
Day 1 of Cycles 2, 4, 8, 12, and 16	Prior to atezolizumab infusion	Atezolizumab PK and ADA (serum)
Day 15 of Cycle 3	Prior to atezolizumab infusion	Atezolizumab PK and ADA (serum)
	Prior to cobimetinib dose	Cobimetinib PK (plasma)
	30 ( $\pm$ 10) minutes following end of atezolizumab infusion	Atezolizumab PK and ADA (serum)
	2–4 hours after cobimetinib dose	Cobimetinib PK (plasma)
Atezolizumab treatment discontinuation visit	At visit	Atezolizumab PK and ADA (serum)
> 90 days after last atezolizumab infusion	At visit	Atezolizumab PK and ADA (serum)

ADA= anti-drug antibody; NA= not applicable; PK= pharmacokinetic.

Notes: Except for Day 1 of Cycle 1 all other study visits and assessments during the treatment period should be performed within  $\pm$ 3 days of the scheduled date.

Study assessments may be delayed or moved ahead of the window to accommodate holidays, vacations, and unforeseen delays.

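### Section 6.7: if efficacy is compared by any-time ADA status, the comparison leans toward ADA-positive patients doing better, by an amount that depends on when ADAs arise

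*Combined protocol and SAP*

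**What the plan says.** Section 6.7 defines the population ("The immunogenicity analyses will include patients with any ADA assessment") and a single status per patient. A patient who is negative or missing at baseline becomes positive on any later ADA response, with no time limit. To be negative, that patient must "have a post-baseline ADA result, and all post-baseline samples are negative". A patient positive at baseline becomes positive on a fourfold titer rise in any later sample. Counts cover results "during both the treatment and follow-up periods". The section then adds: "The relationship between ADA status and safety, efficacy, PK, and biomarker endpoints may be analyzed and reported descriptively via subgroup analyses". This serves an exploratory objective in Table 2, whose endpoint is "Relationship between ADA status and efficacy, safety, or PK endpoints".

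Appendix 2 schedules post-baseline ADA samples at "Day 1 of Cycles 2, 4, 8, 12, and 16", at Day 15 of Cycle 3, at the atezolizumab discontinuation visit, and more than 90 days after the last infusion. Under Section 3.1.1.1, treatment lasts until unacceptable toxicity or loss of clinical benefit. Section 6.4.2 starts OS and PFS at enrollment. Section 6.7 gives no landmark, no time-dependent status, no cut-off for classification and no allowance for unequal exposure, although Section 6.5 does plan exposure-adjusted rates for selected adverse events.

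**The concern.** The label uses information from after enrollment, but the survival clock starts at enrollment. A patient who converts at Cycle 8 must have lived and stayed in sampling until then, and that time is credited to the ADA-positive group. A patient who progresses at the first scan has few chances to convert and is more likely to be labelled negative. ORR and DCR have no time origin but show the same selection, because responders are treated and sampled longer. DOR starts at response, so the enrollment-clock argument does not apply to it.

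At stake is the reading of one exploratory objective. A table by ADA status could suggest that ADAs are harmless or favorable when the pattern comes from sampling alone.

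**Working it through.** **Figures in the plan.** The only sample-size total is up to about 250: 6 × 40 + 12 = 252, which agrees. The titer rule also agrees: log10(4) = 0.602, against 0.60 titer units. The plan states no ADA incidence, onset time or size for the ADA comparison, so these are assumptions, shown as ranges.

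**Sampling opportunity.** With 28-day cycles, Cycle c Day d is study day 28(c − 1) + d. The scheduled on-treatment samples fall on days 29, 71, 85, 197, 309 and 421. A patient stopping at the first 8-week scan (about day 56) gives one of them; a patient treated through day 421 gives six. The post-treatment sample needs survival to more than 90 days after the last infusion.

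**Simulation with no ADA effect** (400,000 patients per scenario), scaled near the urothelial benchmark in Section 1.1.2 (median PFS 2.1 months, OS 7.9 months):

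- Progression: exponential, median 38 days, detected at the next 56-day scan. Death: exponential, mean 230 days after progression. Toxicity stop: 0.01 per month. Response: 90% of patients with PFS of at least 112 days.
- Realised values: median PFS 1.8 months, median OS 7.2 months, ORR about 12%.
- ADA onset is independent of progression and death. Assumed attendance is 80% at discontinuation and 50% of survivors at the later visit.
- Status follows Section 6.7. Patients never sampled after baseline are in neither group.

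| ADA onset | PFS HR | OS HR | Median OS, ADA+ / ADA− (months) | ORR, ADA+ / ADA− |
|---|---|---|---|---|
| All by Cycle 2 Day 1 (30% convert) | 1.00 | 1.00 | 7.4 / 7.4 | 11.9% / 12.0% |
| Median 3 weeks (40% susceptible) | 0.93 | 0.93 | 7.8 / 7.2 | 13.0% / 11.3% |
| Median 6 weeks (40%) | 0.87 | 0.88 | 8.2 / 7.0 | 14.8% / 10.8% |
| Median 12 weeks (50%) | 0.80 | 0.82 | 8.7 / 6.9 | 17.1% / 10.1% |
| Constant hazard, median 52 weeks | 0.74 | 0.79 | 9.2 / 7.0 | 20.9% / 10.1% |
| Constant hazard, median 26 weeks | 0.72 | 0.77 | 9.0 / 6.6 | 19.4% / 8.5% |

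The last four rows give ORR differences of 4.0, 7.0, 10.8 and 10.9 points. A separate simulation under the same Section 6.7 rule gave PFS HR 0.72–0.83, OS HR 0.75–0.86 and 3–9 points for spread-out onset. A model with patient heterogeneity and longer treatment gave larger bias at the late-onset end (PFS HR down to 0.46, OS HR 0.54). In that model, full attendance at both post-treatment visits did not remove the bias (median onset 6 weeks: PFS 0.88, OS 0.87).

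**Remedies, first model.** A landmark at day 29 gives HR 1.00 for PFS and 0.99–1.00 for OS in every row. ADA as a time-dependent covariate from the first positive sample gives PFS HR 1.00–1.01. ORR by day-29 status, among patients sampled then, is about 12% in both groups.

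**Noise in one cohort.** With 30% positive and ORR 15%, the standard error of the ORR difference is √[0.15 × 0.85 × (1/n₊ + 1/n₋)]. For 20 patients (6 and 14) it is about 17 points; for 40 patients (12 and 28), about 12 points.

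**Cohort 7.** Atezolizumab starts on day 15 (Section 4.3.2.2), so Cycle 2 Day 1 is 29 − 15 = 14 days after first exposure, against 28 days in Cohorts 1–6.

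**The case against.** The analysis is optional, descriptive and tied to an exploratory objective. Section 6.1 calls the study hypothesis generating and plans no testing. All of this is true and limits the weight of the point. A descriptive table carries the same bias, however, and leaving out a test does not remove it.

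Results are presented by cohort, and the standard errors above are as large as the bias or larger. This also stands: noise can reverse the direction in any one cohort. But the bias is systematic. In the heterogeneous model the OS hazard ratio fell below 1 in 68% to 97% of null cohorts of 40 for the four later-onset scenarios, against 48% when all onset was early. Section 6.7 also summarizes ADA counts by treatment group, so pooling, which would reduce the noise but not the bias, is possible.

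The hazard ratio is not a planned output; Section 6.4.2 specifies Kaplan-Meier medians. It serves here as a yardstick, and the medians in the table shift the same way.

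A reader might infer more than the documents support:

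- *That ADAs will look protective whatever happens.* With all onset before the first post-dose sample there is essentially no bias. Counting never-sampled patients as negative gives an early-onset HR of about 0.95, but Section 6.7 does not count patients negative or missing at baseline that way.
- *That the objective is to detect a loss of efficacy.* Table 2 states no direction.
- *That the main result is affected.* The primary ORR analysis does not use ADA status.

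**Conclusion.** The point holds in a conditional form. If efficacy is reported by the any-time ADA status of Section 6.7, the comparison favors ADA-positive patients whenever some ADAs arise after the first post-baseline sample. Under no true effect the bias runs from essentially none to a hazard ratio of roughly 0.72–0.88 and an ORR about 3 to 11 points higher when onset is spread over weeks to months; greater heterogeneity makes it larger. These sizes rest on assumed ADA incidence, onset, visit attendance and post-progression survival. The direction rests only on the classification rule, the sampling schedule and the time origin, all of which are in the text. This is a modest but worthwhile correction to an exploratory analysis.

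**What to change.** In Section 6.7, keep the any-time definition for ADA incidence and add a separate rule for efficacy by ADA status:

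- **OS and PFS, Cohorts 1–6:** classify by the Cycle 2 Day 1 sample and count time from that visit, among patients still at risk (alive for OS; alive and progression free for PFS). Alternatively, use ADA as a time-dependent covariate from the first positive sample.
- **ORR:** use status at Cycle 2 Day 1, which precedes the first scheduled 8-week scan. Do not use a Cycle 4 Day 1 landmark for ORR, because restricting to patients not yet responding drops week-8 responders.
- **Cohort 7:** use time-dependent status or a later landmark for OS and PFS, because Cycle 2 Day 1 is only about 14 days after the first atezolizumab dose.
- **Reporting:** give the number in each ADA group, and say that differences within a single cohort are imprecise.

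The cost is wording and programming; the samples and dates are already scheduled. The downside is that later converters count as negative in the landmark analysis, and patients no longer at risk at the landmark leave it.
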